1.5 Study rationale

Adoptive cellular immunotherapy with ex vivo manipulated autologous immune cells has been an attractive approach to refractory cancers. Cbl-b is a major negative regulator of immune function. Adoptive cellular immunotherapy with Cbl-b silenced cells significantly

Safety and Immunologic Activity of Multiple Infusions of APN401

Wake Forest Baptist Comprehensive Cancer Center

CCCWU 03716

decreased tumor burden in mouse models without toxicity. Multiple infusions were applied in these studies. APN401 is a suspension of autologous human PBMCs transfected *ex vivo* with a siRNA that silences Cbl-b developed for adoptive cellular immunotherapy applications. A phase I clinical trial to determine the toxicities of a single intravenous administration of APN401 established feasibility and safety. This clinical trial will examine multiple infusions and also provide an initial estimate of immunologic activity. The overall goal is to determine if there is sufficient evidence of safety and immunologic activity to proceed to phase II clinical trials, alone or in combination with other antitumor agents.

2.0 Objectives

2.1 Primary

- 2.1.1 To determine the toxicities and establish the safety of multiple infusions of APN401

2.2 Secondary

- 2.2.1 To determine the immunologic effects of multiple infusions of APN401
- 2.2.2 To document clinical response and survival

3.0 Selection of Patients

3.1 Inclusion criteria

- 3.1.1 Patients with histologically confirmed inoperable, recurrent or metastatic malignant solid tumors, deemed incurable, and who have either:
 - failed to respond to standard therapy or
 - for whom no standard therapy is available or
 - refuse to receive standard therapies

The study is intended to enroll patients with pancreatic and colorectal cancer. Patients with other types of solid tumors will require approval by the Principal Investigator.

- 3.1.2 Measurable disease as defined by RECIST (see Section 9.0)
- 3.1.3 Patients with treated, stable, and asymptomatic brain metastases are eligible
- 3.1.4 Patients on every 2, 3 or 4 week systemic therapy programs must be off the treatment program for at least 2, 3, or 4 weeks, respectively, and must have recovered from any clinically significant toxicity experienced. Patients on weekly or daily systemic therapy programs and patients receiving radiation must be at least 1 week since treatment and recovered from any clinically significant toxicity experienced. Must be at least 4 weeks and have recovered from major surgery

Safety and Immunologic Activity of Multiple Infusions of APN401

Wake Forest Baptist Comprehensive Cancer Center

CCCWU 03716

3.1.5 Age \geq 18 years

3.1.6 ECOG performance status 0 or 1

3.1.7 Patients must have the following lab values obtained $<$ 4 weeks prior to starting treatment:

- WBC \geq 3000/ μ L
- Platelets \geq 100,000/ μ L
- Hematocrit \geq 28%
- Creatinine \leq 1.6 mg/dL
- AST and ALT $<$ 2.5 \times upper limit of normal
- Bilirubin \leq 1.6 mg/dL (except patients with Gilbert's Syndrome, who must have a total bilirubin less than 3.0 mg/dL)
- Albumin \geq 3.0 g/dL
- INR \leq 1.5

3.2 Exclusion criteria

3.2.1 Women must not be pregnant or breastfeeding due to unknown effects of the study treatments on the unborn fetus. All women of childbearing potential must have a blood test within 72 hours to rule out pregnancy. Women of childbearing potential and sexually active males must be strongly advised to use an accepted and effective method of contraception. Women of childbearing potential (WOCBP) must be using an adequate method of contraception to avoid pregnancy throughout the study and for 26 weeks after the last dose of investigational product, in such a manner that the risk of pregnancy is minimized. Sexually mature females who have not undergone a hysterectomy or who have not been postmenopausal naturally for at least 24 consecutive months (i.e., who have had menses at some time in the preceding 24 consecutive months) are considered to be of childbearing potential. Women who are using oral contraceptives, other hormonal contraceptives (vaginal products, skin patches, or implanted or injectable products), or mechanical products such as an intrauterine device or barrier methods (diaphragm, condoms, spermicides) to prevent pregnancy, or are practicing abstinence or where their partner is sterile (e.g., vasectomy) should be considered to be of childbearing potential.

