4.0 Patient Registration

All patients entered on any WFBCCC trial, whether treatment, companion, or cancer control, must be registered with the WFBCCC Protocol Registrar or entered into the Oncology Research Information System (ORIS) Screening Log within 24 hours of Informed Consent.

In order to ensure prompt registration of your patient:

1. Complete the Eligibility Checklist (Appendix A)
2. Complete the Protocol Registration Form (Appendix B)

Safety and Immunologic Activity of Multiple Infusions of APN401
Wake Forest Baptist Comprehensive Cancer Center
CCCWU 03716

3. Alert the WFUHS registrar by phone, and then send the signed Informed Consent Form, Eligibility Checklist and Protocol Registration Form to the registrar, either by fax or e-mail. Ensure that the "source documents" column of the checklist is complete and that the form is signed by either the research nurse or CRA. Patients will not be registered if forms are incomplete.

Protocol Registrar Contact Information:

[contact]
[contact]
E-MAIL ([contact])

*Protocol Registration is open from 8:30 AM - 4:00 PM, Monday-Friday.

To complete the registration process, the Registrar will assign a patient study number, randomize the patient, and register the patient to the study.

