5.7 Duration of follow-up

All patients, including those who discontinue protocol therapy early, will be followed for response until progression or one year from registration, whichever occurs first. Patients will then be followed for survival for five years from the date of registration. All patients must also be followed through completion of all protocol therapy.

Safety and Immunologic Activity of Multiple Infusions of APN401
Wake Forest Baptist Comprehensive Cancer Center
CCWFU 03716

6.0

Study Calendar

Baseline evaluations, including imaging, are to be conducted within 4 weeks prior to initiation of treatment (Day 0). In the event that the patient's condition is deteriorating, laboratory evaluations should be repeated within 48 hours prior to initiation of the next cycle of therapy.

		Treatment Phase							Follow-Up Phase		Early Termination
	Pre-Study ^J	Day 0 Week 1	Day 1 Week 1	Day 15 Week 3 (± 1 day)	Day 28 Week 5 (± 3 days)	Day 29 ^N Week 5	Day 56 Week 9 (± 3 days)	Day 57 ^N Week 9	Day 71 Week 10 (± 3 days)	Week 18 and every 8 weeks (± 1 week) ^L	Off Study Visit/Early Termination Visit ^{L,M}
Leukapheresis ^A		X			X		X				
APN401 ^B			X			X		X			
Informed consent	X										
Demographics	X										
Medical history	X										
Concurrent meds		X			X		X		X	X ^O	X
Vital signs ^C	X	X	X	X	X	X	X	X	X	X	X
Physical exam ^Q	X	X		X	X		X		X	X	X
Performance status	X	X		X	X		X		X	X	X
CBC w/diff ^D	X	X		X	X		X		X	X	X
Chemistries ^E	X	X		X	X		X		X	X	X
PT, PTT	X										
HIV, HBV, HCV	X										
βhCG ^F	X										
Adverse events		X	X	X	X	X	X	X			X
Imaging ^G	X								X ^L	X ^K	X ^L
Tumor marker ^H	X								X	X	X
Immune response ^I		X		X	X		X			X	X

A. PBMC will be harvested from the peripheral blood by a standard 1.5 to 2.0 blood volume mononuclear cell leukapheresis.

B. APN401 is infused 50 x10⁵/kg IV over 30 minutes

C. Vitals signs should include blood pressure, heart rate, temperature, and respiratory rate. At the administration visits, vital signs should also be performed before infusion and 30 and 60 minutes after the end of the infusion.

D. Hemoglobin, hematocrit, white blood cell count, and platelets. The CBC differential includes enumeration of neutrophils, lymphocytes, eosinophils, monocytes, basophils and any abnormal blood cells.

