E. Serum albumin, urea or BUN, creatinine, ALT, AST, LDH, alkaline phosphatase, direct and total bilirubin, glucose, total protein, sodium, potassium, chloride, CO₂, calcium, phosphorus, and uric acid. These labs should be obtained less than 36 hours prior to the treatment.

F. Women of child bearing potential must have a negative serum or urine pregnancy test (minimum sensitivity 25 IU/L or equivalent units of HCG) at screening. A pregnancy test should also be obtained at any time if there are clinical concerns for possible pregnancy.

G. Imaging should include a chest and abdomen CT. Other types of imaging and/or imaging of other sites should be obtained as clinically indicated to document extent of cancer. If restaging imaging indicates partial or complete response, repeat confirmatory imaging should be obtained in 4 weeks (but

Safety and Immunologic Activity of Multiple Infusions of APN401
Wake Forest Baptist Comprehensive Cancer Center
CCCFU 03716

no sooner than 4 weeks).

H. CA19-9 in patients with pancreatic cancer, CEA in patients with colorectal cancer, and other standard-of-care tumor markers as clinically indicated.

Repeat assessment not required if completed within 2 months of pre-study or early termination visit.

I. On Days 0, 28 and 56, the immune response testing will be taken from the leukapheresis product. On Day 15 and in the follow-up phase, collect 30 ml of blood (3 vials) into 10 ml EDTA tubes. If immune response labs have been collected within 4 weeks prior to the off study/ termination visit, re-collection is not required.

J. Peripheral blood laboratory studies performed in order to determine patient eligibility must be performed within 28 days of study entry. Radiographic and other tests performed in order to determine patient eligibility must be performed within 28 days of study entry.

K. Follow-up radiologic procedures used to assess outcome should be performed within 7 working days of the scheduled time.

L. Patients will be observed until objective disease progression or 1 year, whichever occurs first.

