Exclusion Criteria (as outlined in study protocol)	Criteria NOT present	Criteria is present	Source Used to Confirm *

3.2.1 Women must not be pregnant or breastfeeding due to unknown effects of the study treatments on the unborn fetus. All women of childbearing potential must have a blood test within 72 hours prior to randomization to rule out pregnancy. Women of childbearing potential and sexually active males must be strongly advised to use an accepted and effective method of contraception. Women of childbearing potential (WOCBP) must be using an adequate method of contraception to avoid pregnancy throughout the study and for 26 weeks after the last dose of investigational product, in such a manner that the risk of pregnancy is minimized. Sexually mature females who have not undergone a hysterectomy or who have not been postmenopausal naturally for at least 24 consecutive months (i.e., who have had menses at some time in the preceding 24 consecutive months) are considered to be of childbearing potential. Women who are using oral contraceptives, other hormonal contraceptives (vaginal products, skin patches, or implanted or injectable products), or mechanical products such as an intrauterine device or barrier methods (diaphragm, condoms, spermicides) to prevent pregnancy, or are practicing abstinence or where their partner is sterile (e.g., vasectomy) should be considered to be of childbearing potential.
			

3.2.2 Untreated, progressing, or symptomatic brain metastases
			

Safety and Immunologic Activity of Multiple Infusions of APN401
Wake Forest Baptist Comprehensive Cancer Center
CCCWU 03716

3.2.3 Autoimmune disease, as follows: Patients with a history of inflammatory bowel disease are excluded as are patients with a history of symptomatic disease (e.g., rheumatoid arthritis, systemic progressive sclerosis [scleroderma], systemic lupus erythematosus, autoimmune vasculitis [e.g., Wegener's granulomatosis]). Patients with motor neuropathy considered of autoimmune origin (e.g., Guillain-Barre Syndrome and myasthenia gravis) are excluded. Patients with a history of autoimmune thyroiditis are eligible if their current thyroid disorder is treated and stable with replacement or other medical therapy.
			

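### The 72-hour pregnancy test is not counted back from treatment, so a compliant test can be older than 72 hours at Day 0 with no scheduled repeat

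*Combined protocol and SAP*

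**What the plan says.** The pregnancy test appears in three places.

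- Section 3.2.1: "All women of childbearing potential must have a blood test within 72 hours to rule out pregnancy". No reference event follows the 72 hours. The reason given is that effects on the fetus are not known.
- Appendix A, under the same criterion number: these women "must have a blood test within 72 hours prior to randomization to rule out pregnancy". Section 4.0 has the Registrar "assign a patient study number, randomize the patient, and register the patient to the study", so randomization and registration are one step. The synopsis describes an open-label phase I study and section 5.1 gives one regimen.
- Footnote F of the section 6.0 Study Calendar reads: "Women of child bearing potential must have a negative serum or urine pregnancy test (minimum sensitivity 25 IU/L or equivalent units of HCG) at screening". The calendar marks βhCG in the Pre-Study column only.

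Two general windows also apply. The introduction to section 6.0 says "Baseline evaluations, including imaging, are to be conducted within 4 weeks prior to initiation of treatment (Day 0"). Footnote J says "Peripheral blood laboratory studies performed in order to determine patient eligibility must be performed within 28 days of study entry", which counts from entry and not from treatment. On the order of events, section 4.0 says "Patients will not be registered if forms are incomplete", so the checklist test comes before registration.

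**The concern.** A pregnancy test is informative for a short time. What matters for fetal safety is how old the negative result is when treatment begins. The protocol chose 72 hours for the test, but the only event it attaches to those hours is registration. No passage directly limits the time from registration to Day 0. Section 5.1.1 lets leukapheresis and infusion slip by up to 3 weeks without saying whether this covers the first cycle, and attaches no repeat pregnancy test to a delay.

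Other laboratory tests are treated differently. Section 3.1.7 ties its listed values to less than "4 weeks prior to starting treatment", and footnote E ties the chemistries to under 36 hours before treatment. The pregnancy test is in neither list.

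At stake is an early, unsuspected pregnancy that goes undetected before first exposure. Contraception (3.2.1), reporting of suspected pregnancy (5.6.3) and testing on clinical concern (5.6.3, footnote F) lower that risk. They would not pick up a pregnancy that nobody suspects.

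**Working it through.** The plan gives no figure to reproduce. The check sets the time limits side by side and then counts days.

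| Place | Covers | Limit | Counted back from |
|---|---|---|---|
| 3.2.1 | blood pregnancy test | 72 hours | nothing stated |
| Appendix A | blood pregnancy test | 72 hours | randomization, in effect registration |
| 6.0, footnote F | serum or urine pregnancy test | no hours | done at screening |
| 6.0, introduction | all baseline evaluations | 4 weeks | Day 0 |
| 6.0, footnote J | eligibility tests | 28 days | study entry |
| 3.1.7 | listed labs, no pregnancy test | under 4 weeks | start of treatment |
| 6.0, footnote E | chemistries, no hCG | under 36 hours | treatment |
| 6.0, introduction | laboratory repeat, only if the patient is deteriorating | 48 hours | next cycle |

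Only the 4-week baseline window covers the pregnancy test, counts from treatment and applies unconditionally. The 48-hour repeat also counts from treatment, but it depends on deterioration and does not name hCG.

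**Inputs.** Let a be the days from the test to registration, 0 to 3 (Appendix A, 72 hours = 3 days). Let g be the days from registration to Day 0; the documents do not give it, so a range is shown. Leukapheresis is on Day 0 and infusion 1 on Day 1 (section 6.0).

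**Formulas.** Age of the test at Day 0 = a + g. Age at infusion 1 = a + g + 1. The baseline window requires a + g ≤ 28.

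| g (days) | Oldest test (a = 3): Day 0 / infusion 1 | Newest test (a = 0): Day 0 / infusion 1 |
|---|---|---|
| 0 | 3 / 4 | 0 / 1 |
| 7 | 10 / 11 | 7 / 8 |
| 14 | 17 / 18 | 14 / 15 |
| 25 | 28 / 29 | 25 / 26 |

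**Threshold.** With a = 3 the test is past 72 hours at Day 0 as soon as g exceeds 0. With a = 0 it is past 72 hours once g exceeds 3. So when g is more than 3 days, every test taken before registration is more than 72 hours old at leukapheresis.

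**Cap.** With a = 3, the window gives g ≤ 28 − 3 = 25 days. With a test on the day of registration it gives g ≤ 28. Either way the oldest permitted test is 28 days old at Day 0 and 28 + 1 = 29 days old at infusion 1.

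**Comparison.** If the 72 hours counted back from Day 0, the oldest test at infusion 1 would be 3 + 1 = 4 days. The difference at the outer bound is 29 − 4 = 25 days.

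**The case against.** The strongest reply is that the plan does supply an anchor. Appendix A restates 3.2.1 as 72 hours before the Registrar's step, and no passage says the hours were meant to count from treatment. An eligibility test timed to registration answers an eligibility question, and its later ageing is a consequence of that choice. This stands. A reader might infer that the protocol breaks its own 72-hour limit; it does not, because that limit is never set against treatment.

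A reader might also infer that the three wordings conflict so that staff cannot comply. A negative serum test shortly before registration satisfies all three, so the difference in specimen is a matter of wording. Nor is the gap to Day 0 unlimited: the 4-week window caps it indirectly at about 25 days for the oldest checklist test.

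The size is also hypothetical. Neither g nor the number of women of childbearing potential is given, and that number could be zero among at most 12 patients.

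Finally, for infusions 2 and 3 the plan relies on contraception and clinically indicated testing. A test on Day −3 would be 29 + 3 = 32 days old at infusion 2 and 57 + 3 = 60 days old at infusion 3, before any delay. That is a fair limit on scope. The point here concerns first exposure, the only infusion for which the plan schedules a test at all. It does not imply that later testing is required.

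What the reply does not remove is that following every rule as written does not ensure a recent negative result before infusion 1.

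**Conclusion.** The point holds as a cheap, minor safety improvement. The 72 hours has no event in 3.2.1, runs to registration in Appendix A and is absent from footnote F, while the unconditional limit from treatment is 4 weeks. A fully compliant test can be more than 72 hours old at Day 0, up to 29 days at infusion 1 as an outer bound, with no scheduled repeat.

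This assumes that randomization in Appendix A means registration, and that no limit from registration to Day 0 stands in the Protocol Registration Form (Appendix B), which is not in the text reviewed. The documents do not support reading 29 days as typical, or concluding that any patient was or will be infused on an old test. Sample size, stopping rules and analyses are unaffected.

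**What to change.** Make two changes and keep their anchors separate.

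1. **Eligibility rule.** State it the same way in 3.2.1, Appendix A and footnote F: a negative serum test within 72 hours before registration. In Appendix A, replace randomization with registration.
2. **Treatment-day rule.** In footnote F, with a conditional βhCG mark at Day 0 in the calendar: if the eligibility test is more than 72 hours old at Day 0, repeat hCG with the Day 0 bloods and have a negative result before infusion 1.

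The eligibility item can then be completed before registration as section 4.0 requires, and a test at infusion 1 is at most 3 + 1 = 4 days old.

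The cost is wording in three places, one calendar cell and at most one inexpensive extra assay per woman of childbearing potential. No visit is added, since CBC and chemistries are already marked on Day 0. The result must be back by Day 1. A positive result reported after collection would mean one unneeded leukapheresis but no infusion.

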3.2.2 Untreated, progressing, or symptomatic brain metastases

3.2.3 Autoimmune disease, as follows: Patients with a history of inflammatory bowel disease are excluded as are patients with a history of symptomatic disease (e.g., rheumatoid arthritis, systemic progressive sclerosis [scleroderma], systemic lupus erythematosus, autoimmune vasculitis [e.g., Wegener's granulomatosis]). Patients with motor neuropathy considered of autoimmune origin (e.g., Guillain-Barre Syndrome and myasthenia gravis) are excluded. Patients with a history of autoimmune thyroiditis are eligible if their current thyroid disorder is treated and stable with replacement or other medical therapy.

3.2.4 Any other malignancy from which the patient has been disease-free for less than 2 years, with the exception of adequately treated and cured basal or squamous cell skin cancer, superficial bladder cancer or carcinoma *in situ* of the cervix.

Safety and Immunologic Activity of Multiple Infusions of APN401
Wake Forest Baptist Comprehensive Cancer Center
CCCWU 03716

- 3.2.5 Other ongoing systemic therapy for cancer, including any other experimental treatment. These include concomitant therapy with any of the following: IL-2, interferon, ipilimumab, pembrolizumab, nivolumab, or other immunotherapy; cytotoxic chemotherapy; and targeted therapies.
- 3.2.6 Ongoing requirement for an immunosuppressive treatment, including the use of glucocorticoids or cyclosporine, or with a history of chronic use of any such medication within the last 4 weeks before enrolment. Patients are excluded if they have any concurrent medical condition that requires the use of systemic steroids (the use of inhaled or topical steroids is permitted).
- 3.2.7 Infection with HIV. Due to the mechanism of action of APN401, activity and side effects in an immune compromised patient are unknown.
- 3.2.8 Active infection with Hepatitis B. Active or chronic infection with Hepatitis C.
- 3.2.9 Clinically significant pulmonary dysfunction, as determined by medical history and physical examination. Patients with a history of pulmonary dysfunction must have pulmonary function tests with a $FEV_1 \geq 60\%$ of predicted and a $DLCO \geq 55\%$ (corrected for hemoglobin)
- 3.2.10 Clinically significant cardiovascular abnormalities (e.g., congestive heart failure or symptoms of coronary artery disease), as determined by medical history and physical examination. Patients with a history of cardiac disease must have a normal cardiac stress test (treadmill, echocardiogram, or myocardial perfusion scan) within the past 6 months of study entry.
- 3.2.11 Active infections within 48 hours of study entry
- 3.2.12 Systemic infection requiring chronic maintenance or suppressive therapy
- 3.2.13 Patients are excluded for any underlying medical or psychiatric condition, which in the opinion of the investigator, will make treatment hazardous or obscure the interpretation of adverse events, such as a condition associated with frequent rashes or diarrhea.

4.0 Patient Registration

All patients entered on any WFBCCC trial, whether treatment, companion, or cancer control, must be registered with the WFBCCC Protocol Registrar or entered into the Oncology Research Information System (ORIS) Screening Log within 24 hours of Informed Consent.

In order to ensure prompt registration of your patient:

1. Complete the Eligibility Checklist (Appendix A)
2. Complete the Protocol Registration Form (Appendix B)

Safety and Immunologic Activity of Multiple Infusions of APN401
Wake Forest Baptist Comprehensive Cancer Center
CCCWU 03716

3. Alert the WFUHS registrar by phone, and then send the signed Informed Consent Form, Eligibility Checklist and Protocol Registration Form to the registrar, either by fax or e-mail. Ensure that the "source documents" column of the checklist is complete and that the form is signed by either the research nurse or CRA. Patients will not be registered if forms are incomplete.

Protocol Registrar Contact Information:

[contact]
[contact]
E-MAIL ([contact])

*Protocol Registration is open from 8:30 AM - 4:00 PM, Monday-Friday.

To complete the registration process, the Registrar will assign a patient study number, randomize the patient, and register the patient to the study.

